7.2.9.2 Dose Modification

Pembrolizumab will be withheld for drug-related Grade 4 haematological toxicities, and non-haematological toxicity \geq Grade 3 including laboratory abnormalities, and severe or life-threatening AEs as per Table 8 below.

In case toxicity does not resolve to Grade 0-1 within 12 weeks after last infusion, trial treatment should be discontinued after consultation with the Sponsor. With Investigator and Sponsor agreement, patients with a laboratory AE still at Grade 2 after 12 weeks may continue treatment in the trial only if asymptomatic and controlled. For information on the management of AEs, see Section 6 and Table 8.

Patients who experience a recurrence of the same severe or life-threatening event at the same grade or greater with re-challenge of pembrolizumab should be discontinued from trial treatment.

Events of Clinical interest (ECI) can be potential irAEs and dose modifications for these toxicities should they occur can be found in Appendix 5.

Dosing interruptions are permitted in the case of medical / surgical events or logistical reasons not related to study therapy (e.g., elective surgery, unrelated medical events, patient vacation, and/or holidays). Subjects should be placed back on study therapy within 3 weeks of the scheduled interruption, unless otherwise discussed with the Sponsor. The reason for interruption should be documented in the patient's study record.

Table 8: Dose modification guidelines for drug-related adverse events.

Toxicity	Hold Treatment for Grade	Timing for Restarting Treatment	Treatment Discontinuation
Diarrhoea/Colitis	2-3	Toxicity resolves to Grade 0-1/baseline.	Toxicity does not resolve within 12 weeks of last dose or inability to reduce corticosteroid to 10 mg or less of prednisone or equivalent per day within 12 weeks.
	4	Permanently discontinue	Permanently discontinue
AST, ALT, or Increased Bilirubin	2	Toxicity resolves to Grade 0-1	Toxicity does not resolve within 12 weeks of last dose.
	3-4	Permanently discontinue (see exception below) ¹	Permanently discontinue
Type 1 diabetes mellitus (if new onset) or Hyperglycemia	T1DM or 3-4	Hold pembrolizumab for new onset Type 1 diabetes mellitus or Grade 3-4 hyperglycemia associated with evidence of beta cell failure.	Resume pembrolizumab when patients are clinically and metabolically stable.

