Hypophysitis	2-4	Toxicity resolves to Grade 0-1. Therapy with pembrolizumab can be continued while endocrine replacement therapy is instituted	Toxicity does not resolve within 12 weeks of last dose or inability to reduce corticosteroid to 10 mg or less of prednisone or equivalent per day within 12 weeks.
Hyperthyroidism	3	Toxicity resolves to Grade 0-1	Toxicity does not resolve within 12 weeks of last dose or inability to reduce corticosteroid to 10 mg or less of prednisone or equivalent per day within 12 weeks.
	4	Permanently discontinue	Permanently discontinue
Hypothyroidism		Therapy with pembrolizumab can be continued while thyroid replacement therapy is instituted	Therapy with pembrolizumab can be continued while thyroid replacement therapy is instituted.
Infusion Reaction	3-4	Permanently discontinue	Permanently discontinue
Pneumonitis	2	Toxicity resolves to Grade 0-1. If recurrent grade 2 pneumonitis occurs pembrolizumab should be permanently discontinued.	Toxicity does not resolve within 12 weeks of last dose or inability to reduce corticosteroid to 10 mg or less of prednisone or equivalent per day within 12 weeks.
	3-4	Permanently discontinue	Permanently discontinue
Renal Failure or Nephritis	2	Toxicity resolves to Grade 0-1	Toxicity does not resolve within 12 weeks of last dose or inability to reduce corticosteroid to 10 mg or less of prednisone or equivalent per day within 12 weeks.
	3-4	Permanently discontinue	Permanently discontinue
Hepatitis	1	Continue treatment	
	2 - 4	Withhold treatment	Treat with steroids (prednisone 1 – 2 mg/kg or equivalent). Restart treatment when all liver function tests are down to grade 1 and steroid dose is down to 10 mg or less of prednisone or equivalent. Based on severity and symptoms you may wish to discontinue treatment.
Myocarditis	1 – 2	Withhold treatment	Treat with steroids (prednisone 1 – 2 mg/kg or equivalent). Restart treatment when symptoms are down to grade 1 and steroid dose is down to 10 mg or less of prednisone or equivalent.
	3-4	Permanently discontinue	Permanently discontinue
Skin reactions	1 – 2	Continue treatment	Manage with topical corticosteroids and oral anti-purpuras
	3	Withhold treatment	Treat with steroids (prednisone 1 – 2 mg/kg or equivalent). Restart treatment when rash is down to grade 1 and steroid dose is down to 10 mg or less of prednisone or equivalent.

Toxicity	Hold Treatment for Grade	Timing for Restarting Treatment	Treatment Discontinuation

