	4	Permanently discontinue	Permanently discontinue
Confirmed Stevens-Johnson Syndrome or Toxic-epidermal Necrolysis	-	Permanently discontinue	Permanently discontinue
All Other Drug-Related Toxicity ²	3 or Severe	Toxicity resolves to Grade 0-1	Toxicity does not resolve within 12 weeks of last dose or inability to reduce corticosteroid to 10 mg or less of prednisone or equivalent per day within 12 weeks.
	4	Permanently discontinue	Permanently discontinue

Note: Permanently discontinue for any severe or Grade 3 drug-related AE that recurs or any life-threatening event.

¹ For patients with liver metastasis who begin treatment with Grade 2 AST or ALT, if AST or ALT increases by greater than or equal to 50% relative to baseline and lasts for at least 1 week then patients should be discontinued.

² Patients with intolerable or persistent Grade 2 drug-related AE may hold study medication at physician discretion. Permanently discontinue study drug for persistent Grade 2 adverse reactions for which treatment with study drug has been held, that do not recover to Grade 0-1 within 12 weeks of the last dose.

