irAE	Withhold/Discontinue Pembrolizumab?	Supportive Care
Grade 1	No action	Provide symptomatic treatment
Grade 2	May withhold pembrolizumab. For recurrent grade 2 pneumonitis, pembrolizumab should be discontinued permanently.	Consider systemic corticosteroids in addition to appropriate symptomatic treatment. Steroid taper should be considered once symptoms improve to Grade 1 or less and tapered over at least 4 weeks. Based on limited data from clinical studies in subjects whose immune-related adverse reactions could not be controlled with corticosteroid use, administration of other systemic immunosuppressants can be considered.
Grade 3 and Grade 4	Withhold pembrolizumab Discontinue if unable to reduce corticosteroid dose to < 10 mg per day prednisone equivalent within 12 weeks of toxicity	Systemic corticosteroids are indicated in addition to appropriate symptomatic treatment. May utilize 1 to 2 mg/kg prednisone or equivalent per day. Steroid taper should be considered once symptoms improve to Grade 1 or less and tapered over at least 4 weeks. Based on limited data from clinical studies in subjects whose immune-related adverse reactions could not be controlled with corticosteroid use, administration of other systemic immunosuppressants can be considered.
Please Note: If an irAE does not resolve or improve to \leq Grade 1 within 12 weeks after last administration of pembrolizumab, study therapy discontinuation should be considered after discussion with a Merck Clinical Director via the RM-CTU trial manager.		

Details for managing specific irAEs are summarised below:

Immune-mediated pneumonitis

Monitor subjects for signs and symptoms of pneumonitis. If pneumonitis is suspected, evaluate with radiographic imaging and exclude other causes. Administer corticosteroids for Grade 2 or greater events (initial dose of 1-2 mg/kg/day prednisone or equivalent followed by a taper), withhold pembrolizumab for moderate (Grade 2) pneumonitis, and permanently discontinue pembrolizumab for recurrent moderate (Grade 2), severe (Grade 3) or life-threatening (Grade 4) pneumonitis.

Immune-mediated colitis

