Monitor subjects for signs and symptoms of colitis and exclude other causes of colitis. Administer corticosteroids for Grade 2 (if persists for >3 days) or greater events (initial dose of 1-2 mg/kg/day prednisone or equivalent followed by a taper), withhold pembrolizumab for moderate (Grade 2) or severe (Grade 3) colitis, and permanently discontinue pembrolizumab for life-threatening (Grade 4) colitis.

Immune-mediated hepatitis

Monitor subjects for changes in liver function (at the start of treatment, periodically during treatment and as indicated based on clinical evaluation) and symptoms of hepatitis, and exclude other causes of hepatitis. Administer corticosteroids (initial dose of 0.5 – 1.0 mg/kg/day for grade 2 events, and 1 – 2 mg/kg/day for grade 3 or greater events, of prednisone or equivalent, followed by a taper) and, based on severity of liver enzyme elevations, withhold or discontinue pembrolizumab.

Immune-mediated nephritis

Monitor patients for changes in renal function and exclude other causes of nephritis. Administer corticosteroids for grade 2 or greater events (initial dose of 1 – 2 mg/kg/day prednisone or equivalent, followed by a taper), withhold pembrolizumab for moderate (Grade 2), and permanently discontinue pembrolizumab for severe (Grade 3) or life-threatening (Grade 4) nephritis.

Immune-mediated endocrinopathies

Monitor subjects for signs and symptoms of hypophysitis (including hypopituitarism and secondary adrenal insufficiency) and exclude other causes of hypophysitis. Administer corticosteroids to treat secondary adrenal insufficiency and other hormone replacement as clinically indicated, withhold pembrolizumab for moderate (Grade 2), withhold or discontinue pembrolizumab for severe (Grade 3) or for life-threatening (Grade 4) hypophysitis.

Monitor subjects for hyperglycemia or other signs and symptoms of type 1 diabetes. Exclude other causes of diabetes. Administer insulin for type 1 diabetes, and withhold pembrolizumab in cases of severe hyperglycemia until metabolic control is achieved.

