	Grade 2	
 Withhold pembrolizumab, may restart if Grade 1 or resolved within 12 weeks Consider Haematology consultation 	
 Prednisone 1-2mg/kg daily Permanently discontinue pembrolizumab if dose cannot be reduced to prednisone 10mg or less or equivalent per day within 12 weeks.
	Grade 3	
 Withhold pembrolizumab, may restart if Grade 1 or resolved within 12 weeks Recommend Haematology consultation 	
 IV methylprednisolone 125mg or Prednisone 1-2mg/kg p.o. (or equivalent) as appropriate. Permanently discontinue pembrolizumab if corticosteroid dose cannot be reduced to prednisone 10mg or less or equivalent per day within 12 weeks.
	Grade 4	
 Discontinue pembrolizumab Recommend Haematology consultation 	
 IV methylprednisolone 125mg or Prednisone 1-2mg/kg p.o. (or equivalent) as appropriate.
Hepatic – Drug induced Liver Injury (DILI). Please refer to Section 6 and 7 for definitions of (DILI)	Grade 1 (Asymptomatic)	
 No action 	
 Intervention not indicated
	Grade 2	
 Report liver toxicity ECIs within 24 hours, as detailed in Section 7.5.2. Withhold Pembrolizumab if AST or ALT >3.0 to 5.0 X ULN and/or total bilirubin is >1.5 to 3.0 X ULN Monitoring Liver function until values return to baseline 	
 0.5-1mg/kg/day methylprednisolone 125mg or oral equivalent. LFT grade 1 or less initiate steroid taper for no less than 4 weeks. Consider prophylactic antibiotics and resume pembrolizumab. Permanently discontinue pembrolizumab if dose cannot be reduced to prednisone 10mg or less or equivalent per day within 12 weeks.

			
 Permanently discontinue pembrolizumab for patients with liver mets who begin treatment with grade 2 elevation of AST or ALT and AST or ALT increase $\geq 50\%$ relative to baseline and lasts ≥ 1 week.

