	Grade 3	
 Report liver toxicity ECIs within 24 hours, as detailed in Section 8.5.2. Discontinue pembrolizumab if AST or ALT $> 5.0 \times$ ULN and/or total bilirubin is $> 3.0 \times$ ULN Consider consultation and biopsy to establish aetiology 	
 High dose IV glucocorticosteroids for 24-48hours. Symptoms grade 1 or less initiate steroid taper for no less than 4 weeks 
 prednisone 1 to 2 mg/kg/day or dexamethasone 4mg every 4 hours. If serum transaminase levels do not decrease or symptoms worsen please refer to Section 7 and 8. Permanently discontinue pembrolizumab if dose cannot be reduced to prednisone 10mg or less or equivalent per day within 12 weeks.
	Grade 4	
 Report liver toxicity ECIs within 24 hours, as detailed in Section 8.5.2. Discontinue pembrolizumab 	
 Manage as per grade 3
Myocarditis ¹ ¶ Ensure that other causes of myocarditis are adequately evaluated to exclude other aetiologies	Grade 1 and 2	
 Withhold Pembrolizumab Consider Cardiology consult 	
 Prednisone 1 – 2 mg/kg or equivalent Restart treatment when symptoms are down to grade 1 and steroid dose is down to 10 mg or less of prednisone or equivalent 1-2mg/kg daily of prednisone or equivalent.
	Grade 3 and 4	
 Discontinue Pembrolizumab permanently Obtain Cardiology consult 	
 Prednisone 1 – 2 mg/kg or equivalent Permanently discontinue pembrolizumab
Neurologic	Grade 1 (Asymptomatic)	
 No action 	
 Intervention not indicated
	Grade 2	
 Consider withholding pembrolizumab Consider Neurology consult and biopsy for diagnosis. 	
 Consider 1-2mg/kg daily of prednisone as appropriate Permanently discontinue pembrolizumab if dose cannot be reduced to prednisone 10mg or less or equivalent per day within 12 weeks.

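### For grade 2 hepatitis, Table 8 gives prednisone 1–2 mg/kg, while section 7.5 and Appendix 5 give 0.5–1 mg/kg/day

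*Protocol*

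**What the plan says.** Three places in the protocol set the steroid dose for hepatitis.

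- **Table 8 (section 7.2.9.2).** Grades 2, 3 and 4 share one row. Pembrolizumab is withheld, and the instruction is "Treat with steroids (prednisone 1 – 2 mg/kg or equivalent). Restart treatment when all liver function tests are down to grade 1", with the steroid also down to 10 mg or less of prednisone. Discontinuation is left as an option that depends on severity and symptoms.
- **Section 7.5, immune-mediated hepatitis.** The dose depends on grade: "initial dose of 0.5 – 1.0 mg/kg/day for grade 2 events, and 1 – 2 mg/kg/day for grade 3 or greater events". Pembrolizumab is withheld or discontinued according to how far the liver enzymes have risen.
- **Appendix 5, hepatic, grade 2.** The entry reads "0.5-1mg/kg/day methylprednisolone 125mg or oral equivalent".

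Section 7.2.9.2 contains two cross-references. One sends the management of adverse events to Section 6 and Table 8. The other says "Events of Clinical interest (ECI) can be potential irAEs and dose modifications for these toxicities should they occur can be found in Appendix 5". Section 7.5 likewise refers drug-associated immune-related events of clinical interest to Appendix 5, and Table 12 (section 8.5.2) counts hepatitis of grade 2 or above as such an event.

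**The concern.** A grade 2 hepatitis falls under all three texts at once, and Table 8 does not agree with the other two. Table 8 is where a clinician looks to decide whether to hold the drug, so its dose is likely to be used. Someone who follows it can start a grade 2 patient on more steroid than section 7.5 allows, with further to taper before reaching the 10 mg that Table 8 requires for restart. Appendix 5 makes the drug permanently discontinued if that level is not reached within 12 weeks.

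Pooling the grades also affects the action at grade 3. The hepatitis row says withhold and restart. The AST, ALT or bilirubin row of the same table says, at grades 3–4, "Permanently discontinue (see exception below". A first grade 3 hepatitis that shows as raised transaminases fits both rows.

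**Working it through.** The protocol has no statistical figure to reproduce here. The check sets the texts side by side and compares the ranges.

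**Step 1. Doses for grade 2 hepatitis**

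| Source | Dose | Grades covered |
|---|---|---|
| Table 8 | prednisone 1–2 mg/kg (interval not stated; read here as daily) | 2–4 together |
| Section 7.5 | 0.5–1.0 mg/kg/day | 2 |
| Appendix 5 | 0.5–1 mg/kg/day, followed by an unexplained 125 mg | 2 |

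For grades 3–4, Table 8 and section 7.5 both give 1–2 mg/kg, so the conflict between them on dose is confined to grade 2.

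**Step 2. Size of the gap between Table 8 and section 7.5**

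- Ratio of the lower ends: 1 / 0.5 = 2.
- Ratio of the upper ends: 2 / 1.0 = 2.
- Overlap of [0.5, 1.0] and [1, 2]: the single value 1 mg/kg.
- Excess of Table 8 over the section 7.5 ceiling: (1 to 2) − 1.0 = 0 to 1 mg/kg.
- Largest excess at assumed body weights (none is given in the protocol): 50 kg × 1 = 50 mg, 70 kg × 1 = 70 mg, 100 kg × 1 = 100 mg.
- At 70 kg the full ranges are 70–140 mg under Table 8 and 35–70 mg under section 7.5.

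**Step 3. Which text prevails**

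Table 12 makes the event an ECI, and sections 7.2.9.2 and 7.5 route such events to Appendix 5, whose range agrees with section 7.5. Against that, section 7.2.9.2 also names Table 8 for adverse events generally, and the Appendix 5 line is not clean. Table 10 does not help, because section 7.5 limits it to events not detailed elsewhere. The lower dose is therefore favoured, but the protocol does not state that it overrides Table 8.

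**Step 4. Which text looks wrong**

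Section 7.5 starts other organs at the higher dose from grade 2. For pneumonitis it says "Administer corticosteroids for Grade 2 or greater events (initial dose of 1-2 mg/kg/day prednisone or equivalent followed by a taper", and colitis and nephritis also start at 1–2 mg/kg/day. Only hepatitis has a separate, lower grade 2 dose. Appendix 5 gives 1–2 mg/kg at grade 2 for pneumonitis, colitis, haematologic and renal events, but 0.5–1 for hepatic events. The lower hepatic dose thus looks deliberate and Table 8 looks like the outlier.

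**Step 5. Action at grade 3 or above**

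- Table 8, hepatitis row: withhold, restart on recovery, discontinuation optional.
- Table 8, AST/ALT/bilirubin row: permanent discontinuation. The exception in its footnote concerns patients with liver metastases who begin treatment with grade 2 enzymes.
- Appendix 5, hepatic grade 3: the action column begins "Discontinue pembrolizumab if AST or ALT" and gives enzyme thresholds, but the supportive-care column adds permanent discontinuation if the steroid cannot be tapered within 12 weeks. That condition makes sense only if the drug might be resumed.
- Table 8 note: "Permanently discontinue for any severe or Grade 3 drug-related AE that recurs or any life-threatening event". This covers grade 4 and recurrent grade 3, but not a first grade 3 episode.

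**The case against.** The best counter-argument is that the protocol does give direction. Grade 2 hepatitis is an ECI, ECIs go to Appendix 5, and Appendix 5 agrees with section 7.5. This stands in part. A reader might infer that nothing in the protocol indicates which dose governs, and the documents do not support that. What remains is a competing pointer to Table 8 and an Appendix 5 entry too unclear to settle the matter.

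The outlier argument also has limits. Section 7.4.1.1 gives 0.5 mg/kg/day for persistent grade 2–3 enterocolitis. Appendix 5 uses a fixed 40 mg for hypophysitis, and topical steroid first for grade 2 ocular and skin events. The pattern in step 4 is evidence, not proof.

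On grade 3, a reader might infer that the protocol plainly requires discontinuation and that the hepatitis row is simply wrong. The taper condition in Appendix 5 and the withhold-or-discontinue wording of section 7.5 do not support that. The choice is a clinical one.

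A reader might also take the 125 mg in Appendix 5 as an instructed grade 2 dose. It may be a remnant of editing or of the PDF reading, and it is not treated here as a dose.

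Finally, the practical effect is limited. A start at exactly 1 mg/kg satisfies both ranges. Section 7.5 asks for immediate discussion of any irAE of grade 2 or higher with the Chief Investigator or delegate, and section 7.4.1 leaves supportive care to the treating investigator's judgement. These points reduce the risk but do not remove the conflicting instruction.

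**Conclusion.** The point holds as an inconsistency in operative patient-management text. At grade 2, Table 8 gives twice the section 7.5 dose at each end of the range and allows up to 1 mg/kg above its ceiling, or at most 50–100 mg for assumed weights of 50–100 kg. This rests on reading the Table 8 dose as daily.

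The trial treats at most 18 patients. That is only an upper bound on those affected, because the protocol gives no expected rate of grade 2 hepatitis.

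The mismatch at a first grade 3 episode is real within Table 8, but its resolution is for the clinical team. Neither matter touches the DLT definition, the 3+3 decision, the sample size or any planned analysis. It is a minor safety-management correction that should be made.

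**What to change.** 1. Split the Table 8 hepatitis row, subject to clinical confirmation. Grade 2: prednisone 0.5–1 mg/kg/day or equivalent, with withholding and restart as now stated. Grades 3–4: 1–2 mg/kg/day or equivalent.
2. Check the 125 mg in the Appendix 5 hepatic grade 2 entry against its source, and delete it if it is a remnant.
3. Separately, have the clinical team decide the action at a first grade 3 episode, and state it identically in both Table 8 rows and in Appendix 5, including whether the 12-week taper condition stays.

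Section 7.5 can keep its present grade 2 dose. The first two changes cost one table row and one entry check at the next amendment. The third needs a clinical decision before any text is changed.

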Thyroid disorders have been reported in subjects receiving pembrolizumab and can occur at any time during treatment; therefore, monitor subjects for changes in thyroid function (at the start of treatment, periodically during treatment and as indicated based on clinical evaluation) and clinical signs and symptoms of thyroid disorders. Hyperthyroidism may be managed symptomatically. Withhold pembrolizumab for severe (Grade 3) hyperthyroidism, and permanently discontinue pembrolizumab for life-threatening (Grade 4) hyperthyroidism. Hypothyroidism may be managed with replacement therapy without treatment interruption and without corticosteroids. For subjects with severe (Grade 3) or life-threatening (Grade 4) endocrinopathy that improves to Grade 2 or lower and is controlled with hormone replacement, continuation of pembrolizumab may be considered.

Other immune-mediated AEs

The following additional clinically significant, immune-mediated adverse reactions were reported in less than 1% (unless otherwise indicated) of subjects treated with pembrolizumab: uveitis, myositis, Guillain-Barré syndrome, pancreatitis and severe skin reactions (1.1%).

In addition, a set of irAEs have also been classified as immune-related events of clinical interest (irECI) a full list of these can be found in Table 12 in section 8.5.2. Patients with symptomatic irECIs should immediately stop receiving pembrolizumab and be evaluated to rule out non-treatment related causes of the event. Overdose and liver toxicity irECIs irrespective of relationship to the study drug should be reported within 24 hours of the investigator being aware to the Sponsor (via RM-CTU) who will in turn notify MSD. If the irECI is determined to be associated please refer to Appendix 5 for the recommendations on the management of these irECIs. If the event is not considered to be associated with the study drug the physician should exercise individual clinical judgment on the event management based on the patient. Any additional questions of the collection or information on management of irECIs should be directed to the Sponsor (via RM-CTU).

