12.5 Appendix 5 - Identification, Evaluation and Management of immune related events of clinical interest (irECIs)

ECI	Grade	Action to be taken	Supportive Care
Pneumonitis –	Grade 1 (Asymptomatic)	
 No action 	
 Intervention not indicated
	Grade 2	
 Withhold pembrolizumab, may restart if Grade 1 or resolved within 12 weeks Consider bronchoscopy and biopsy/BAL, ID Consult and frequent chest x-ray for monitoring. Conduct in person evaluation twice a week 	
 1-2mg/kg/day prednisone or equivalent. Symptoms grade 1 or less, initiate steroid taper for no less than 4 weeks. Permanently discontinue pembrolizumab if dose cannot be reduced to 10mg prednisone or less or equivalent per day within 12 weeks.
	Grade 3 and 4	
 Discontinue pembrolizumab Hospitalise patient Bronchoscopy with biopsy and/or BAL is recommended. 	
 methylprednisolone 125mg IV. Symptoms grade 1 or less initiate steroid taper for no less than 4 weeks 
 Prednisone 1 to 2 mg/kg/day or dexamethasone 4mg every 4 hours If IV steroids do not reduce initial symptoms within 48-72 hours treat with additional anti-inflammatory measures. At symptom relief discontinue anti-inflammatory and start steroid taper over 45-60 days. If symptoms worsen during this period refer to Section 7 and 8.

 1st episode - May increase dosing interval by one week in subsequent cycles 2nd episode of - Pneumonitis, permanently discontinue pembrolizumab if upon re-challenge patient develops Pneumonitis \geq Grade 2 			
Colitis	Grade 1 (Asymptomatic)	
 No action 	
 Intervention not indicated

–

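### For a first grade 3 hepatitis, the hepatitis row of Table 8 lets pembrolizumab restart, while the AST/ALT/bilirubin row and Appendix 5 say stop

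*Protocol*

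**What the plan says.** Section 7.2.9.2 of the protocol applies Table 8 to drug-related non-haematological toxicity of grade 3 or higher. Table 8 has two rows that concern the liver.

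- **Hepatitis row.** Grades 2 to 4 form one band: withhold, give prednisone 1-2 mg/kg, and then "Restart treatment when all liver function tests are down to grade 1 and steroid dose is down to 10 mg or less", measured as prednisone. Stopping is a matter of judgement: "Based on severity and symptoms you may wish to discontinue treatment".
- **AST, ALT or increased bilirubin row.** Grade 2 is held until grade 0-1. For grades 3-4 the entry is "Permanently discontinue (see exception below", which refers to footnote 1.

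Appendix 5 (hepatic, grade 3) gives the action "Discontinue pembrolizumab if AST or ALT" is above 5 x ULN and/or total bilirubin is above 3 x ULN.

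Two sentences point to Appendix 5. For events of clinical interest, section 7.2.9.2 says that "dose modifications for these toxicities should they occur can be found in Appendix 5". For immune-related events judged to be drug-associated, section 7.5 says "please refer to Appendix 5 for the recommendations on the management of these irECIs".

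**The concern.** The two liver rows are not separate conditions. The hepatitis row uses liver function tests as its restart criterion, and Table 12 (section 8.5.2) puts hepatitis, autoimmune hepatitis and transaminase elevations in one class of hepatic event. A grade 3 event can therefore fall under both rows, and they disagree on whether the patient may be dosed again.

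Patient safety is at stake, in a phase I trial whose primary objective is safety and tolerability. An investigator who follows the hepatitis row may rechallenge a patient whom the neighbouring row says must stop. Two investigators could each comply with the protocol and treat identical patients in opposite ways.

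**Working it through.** The protocol gives no figure on this point to reproduce. The check is one worked case, read against each provision that could apply.

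**Case.** A first drug-related hepatitis with ALT above 5 x ULN (the Appendix 5 grade 3 threshold), no liver metastasis, not life-threatening, recovering to grade 1 on 10 mg prednisone or less.

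| Provision | Instruction for this case |
|---|---|
| Table 8, hepatitis row | Restart; stopping optional |
| Table 8, AST/ALT/bilirubin row | Stop permanently |
| Appendix 5, hepatic grade 3 | Discontinue |
| Note under Table 8 | Not triggered: it covers a grade 3 event that recurs, or a life-threatening event |
| Table 8, footnote 1 | Not triggered: it covers liver metastasis with grade 2 AST or ALT at the start, and is itself a stopping rule |
| Section 7.5, immune-mediated hepatitis | Withhold or stop by severity of enzyme rise; no grade given |
| Section 7.5, symptomatic irECIs | Stop at once and evaluate; silent on restarting |
| Table 10 | Does not apply: it is for irAEs not covered elsewhere |

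The first row contradicts the second and third, and none of the others decides between them. The two pointers to Appendix 5 are cross-references. Section 7.2.9.2 applies both Table 8 and Appendix 5 without ranking them.

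**Scope by grade.**
- Grade 2: both rows withhold and allow restart after recovery, so they are compatible on restarting. They are not consistent on treatment. The hepatitis row gives prednisone 1-2 mg/kg across grades 2-4, while section 7.5 and Appendix 5 give 0.5-1 mg/kg for grade 2.
- Grade 3, first event: contradiction, as above.
- Grade 3, recurrent, and grade 4: the note under Table 8 already requires a permanent stop.

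**Effect on the primary endpoint.** Section 4.2.1 counts a non-haematological toxicity of grade 3 or higher, related to the combination, as a DLT. That holds whether or not the drug is later restarted, so the DLT count does not change.

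**Can the number of patients be estimated?** The only relevant rate is in section 2.2.6.2: grade 3 or higher ALT rise in 1 of 25 patients (4%; exact 95% CI 0.1% to 20.4%). Those patients received 10 mg/kg every 2 weeks without SBRT. Let p be the rate, and f the share of such rises that are grade 3, handled under the hepatitis row and recovered. The protocol does not give f; I assume 0.25 to 1. With 18 patients, the chance of at least one case is 1 - (1 - pf)^18:

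- p = 0.04, f = 0.25: 1 - 0.99^18 = 0.17
- p = 0.04, f = 1: 1 - 0.96^18 = 0.52
- p = 0.0010, f = 0.25: 1 - 0.99975^18 = 0.0045
- p = 0.2035, f = 1: 1 - 0.7965^18 = 0.98

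Once the uncertainty in p is admitted, the range runs from about 0.5% to about 98%, which is no estimate. The expected count is small even at the top of the range: 18 x 0.2035 = 3.7 patients. At 4% it is at most 18 x 0.04 = 0.72.

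**The case against.** The best defence is that the protocol already routes the case. Hepatitis of grade 2 or higher is an event of clinical interest under Table 12, sections 7.2.9.2 and 7.5 both send such events to Appendix 5, and Appendix 5 says discontinue. Two of the three rules say stop. The hepatitis row does not compel a restart, and it sits in a table labelled as guidelines. Section 7.5 also requires immediate discussion of any irAE of grade 2 or higher with the Chief Investigator or delegate, and liver events are reported within 24 hours. A silent rechallenge is unlikely.

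Much of this stands. The routing favours stopping, and the oversight lowers the risk. It does not remove the contradiction: no sentence gives Appendix 5 precedence over a table applied in the same section, and whoever is consulted reads the same conflicting text.

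A reader might go further and infer that Appendix 5 itself permits resumption, because its hepatic grade 3 entry adds "Permanently discontinue pembrolizumab if dose cannot be reduced to prednisone 10mg or less or equivalent per day within 12 weeks". The document does not support that reading. The hepatic, hyperthyroidism and ocular grade 4 entries are all stop instructions, and each takes over its grade 3 management, which contains the same line. It looks like text carried over between entries, not a rule allowing rechallenge.

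**Conclusion.** The contradiction is real and confined to a first grade 3 drug-related hepatitis. For that patient the hepatitis row of Table 8 permits a restart that the AST/ALT/bilirubin row and Appendix 5 rule out. It is an internal inconsistency in dosing instructions that bears on patient safety and on consistent handling of exposure. It should be corrected.

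Two inferences go too far. The first is a definite probability of an affected patient, such as 17% to 52%. That range rests on an assumed share and on one event in 25 under another regimen. All that can be said is that few patients are likely to be affected. The second is that the safety decision in Part A is compromised; it is not, because the DLT definition does not depend on which row is followed.

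The conclusion assumes that the two liver rows overlap, which Table 12 and the hepatitis row's own restart criterion support.

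**What to change.** Split the hepatitis row of Table 8:

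- **Grade 2:** withhold; prednisone 0.5-1 mg/kg, to match section 7.5 and Appendix 5; restart when liver tests are grade 1 and prednisone is 10 mg or less.
- **Grades 3-4:** permanently discontinue.

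State in section 7.2.9.2 that Appendix 5 governs hepatic events of clinical interest, and make the immune-mediated hepatitis text in section 7.5 refer to these grades. This follows the rule that the protocol already gives in two of its three places. If the sponsor does intend rechallenge after grade 3, it should say so and amend the other two rules instead.

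As an optional tidy-up, word the Appendix 5 hepatic grade 3 action as a permanent stop and delete the leftover steroid-taper condition.

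The cost is an amendment to wording, with no effect on sample size, schedule or endpoints.
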